The primary and secondary objectives involve the main treatment effect of each study agent on AMD and cataract endpoints.

1.1 Primary Objectives

- a. To test whether 400 mg of vitamin E reduces the risk of visually-significant AMD.
- b. To test whether 200 µg of selenium reduces the risk of visually-significant AMD.
- c. To test whether 400 mg of vitamin E reduces the risk of cataract.
- d. To test whether 200 µg of selenium reduces the risk of cataract.

1.2 Secondary Objectives

- a. To test whether 400 mg of vitamin E reduces the risk of advanced AMD.
- b. To test whether 200 µg of selenium reduces the risk of advanced AMD.
- c. To test whether 400 mg of vitamin E reduces the risk of cataract surgery and subtypes.
- d. To test whether 200 µg of selenium reduces the risk of cataract surgery and subtypes.

2.0 **BACKGROUND**

Age-related macular degeneration (AMD) and cataract are two leading causes of visual impairment in older Americans. (1) AMD is the leading cause of visual impairment and blindness with an estimated 25% of people over 65 years showing some manifestation of AMD. (1, 2) More than 50% of the adult population in the U.S. aged 75 years and older suffers from visually significant cataract. (1, 3, 4) Treatment options for AMD and cataract are limited and not without important drawbacks. While laser photocoagulation, and more recently photodynamic therapy, have been shown to be of benefit for a minority of patients with advanced AMD, laser treatment merely delays subsequent vision loss, and the long-term effects of photodynamic therapy remain to be determined. (5 - 9) Cataract surgery accounts for a large proportion of Medicare expenditures. (10) Thus, the identification of inexpensive, safe strategies to prevent these common sources of ocular morbidity is of particular public health importance. (1)

Oxidative mechanisms are believed to contribute to the cumulative tissue damage observed in the aging retina and lens. (11, 12) There is also growing evidence that the development of AMD and cataract may be related to dietary habits, and in particular to the level of antioxidant nutrients contained in the diet. However, problems in altering dietary behavior and the need for life-long intervention make this preventive method difficult to implement. Instead, there has been increasing marketing and use of antioxidant supplements, including eye-specific preparations, despite the lack of convincing evidence supporting such usage. The recognition of the importance of oxidative mechanisms in AMD and cataract, together with the increasing consumption of vitamin supplements, led to the National Eye Institute-sponsored Age-Related Eye Disease Study (AREDS). AREDS tested in randomized trials the effects of daily doses of zinc (80 mg) and an antioxidant combination of vitamin E (400 IU), vitamin C (500 mg), and beta-carotene (15 mg) on the progression of AMD, and the effect of the antioxidant combination on the development and progression of lens opacities. The final randomized trial results for AMD, based on an average of 6.3 years of treatment and follow-up, indicated a benefit of zinc alone or in combination with antioxidant vitamins in delaying the progression to advanced AMD in persons at

high risk. (13) The data also suggested a risk reduction of 15 - 20% for those taking antioxidants alone. The results for cataract indicated no apparent effect of the antioxidant combination on development or progression of age-related lens opacities during the 6.3 years of treatment and follow-up. (14)

The findings in AREDS, particularly as they pertain to AMD, are important for the ocular health of the public and can be expected to generate a new wave of enthusiasm for supplementation with antioxidant nutrients. However, important questions remain. For example, the results for AMD in AREDS pertain to progression to advanced disease in persons in the 2 highest risk groups (persons with extensive intermediate size drusen, at least 1 large druse, noncentral geographic atrophy in 1 or both eyes, or advanced AMD or vision loss due to AMD in 1 eye [AMD Categories 3 and 4]). Among the 2,180 participants in the 2 lower risk groups (persons with no AMD or mild or borderline age-related macular features including multiple small drusen, single or nonextensive intermediate drusen and/or pigment abnormalities in 1 or both eyes, and visual acuity of 20/32 or better in both eyes [AMD Categories 1 and 2]), only 20 cases of advanced AMD were noted by year 5. Thus, AREDS had limited power to assess the benefit of supplementation on progression to advanced AMD, or even to earlier stages of AMD, in persons at low risk. Such an evaluation in low risk individuals is needed, however, because early AMD can be associated with some degree of vision loss, but more importantly, is strongly predictive of subsequent development of advanced AMD. (15, 16) Regarding cataract, the AREDS investigators raise the possibility that for many participants, the intervention may have been initiated too late in the disease process, or was of inadequate duration, for it to be effective. Finally, for both AMD and cataract, the individual effects of vitamin E, vitamin C, and beta carotene in the antioxidant formulation could not be evaluated in AREDS, and thus require further study to clarify effects of individual nutrients.

Two antioxidant nutrients thought to offer protection from photo-oxidative damage are vitamin E and selenium. (17) Vitamin E is a powerful intracellular antioxidant that reduces lipid peroxidation, and selenium is an essential trace nutrient that is critical for the activity of glutathione peroxidase, an endogenous antioxidant enzyme that protects cellular molecules against oxidative damage. (17 - 20) Numerous basic research and observational epidemiologic studies suggest a plausible role for these nutrients, in particular vitamin E, in reducing risks of age-related eye disease. In addition, data indicate that activities of vitamin E and selenium (plus selenium-dependent glutathione peroxidase) are complementary and that the supplements could act synergistically to inhibit AMD and cataractogenesis. (21 - 23)

Inclusion of Minorities and Underserved/Uninsured

It is a standing policy of the Southwest Oncology Group to include eligible patients and/or participants of both sexes and all races and ethnicities in all Group clinical trials, except as restricted by specific disease site (e.g., prostate, gynecological). The proposed participant population for the full SELECT study (**S0000**) will consist of males, due to the specific disease site (prostate), and will include minority populations, including, but not limited to, African-Americans, Hispanics, Asian-Americans, as well as medically underserved populations. As African-American males are at higher risk for the development of prostate cancer, an attempt will be made to over-recruit this population through specific recruitment and adherence strategies. Previous minority accrual in Southwest Oncology Group genitourinary and cancer control studies in 1998 and other relevant studies is shown below:

ACCRUAL	Total	White	Black	Hispanic	Other
Committee (1998)					
GU	318	247 (77.7%)	57 (17.9%)	5 (1.6%)	9 (2.8%)
Cancer Control	532	447 (84.0%)	53 (10.0%)	13 (2.4%)	19 (3.6%)
PCPT (1994 - 1997)	18,882	17,272 (91.5%)	702 (3.7%)	497 (2.6%)	411 (2.2%)
Pivot Accrual (1994 - 1997)	578	379 (65.6%)	159 (27.5%)	27 (4.6%)	13 (2.2%)

3.0 DRUG INFORMATION

Drug information is not applicable to this study. This study will use the same agents as the main SELECT protocol (**S0000**).

4.0 STAGING CRITERIA

Staging Criteria are included in Appendix 19.2 of the main SELECT protocol (**S0000**) as a reference for staging participants who develop prostate cancer.

5.0 ELIGIBILITY CRITERIA

SELECT Participant No. _____

Participant's Initials (L,F,M) _____

5.1 The potential **S0000B** (SEE) participant must be a SELECT participant at the time of registration to SEE. Participants may be registered to SEE at any time after SELECT randomization. Participants are registered only after they report an eye event of interest (as outlined in Section 5.2 below).

5.2 The potential participant must report a diagnosis of age-related macular degeneration (AMD) at baseline (contact 010) or at follow-up, or a diagnosis of cataract or a cataract extraction at follow-up. **(Effective November 1, 2009 accrual of new participants based solely on a diagnosis of cataract or a cataract extraction at follow-up is closed.)**

A participant who reported a previous diagnosis of cataract at baseline (contact 010), then reports a cataract event (another cataract diagnosis or a cataract extraction) at follow-up, is not eligible.

A participant who reported a previous diagnosis of cataract at baseline (contact 010), then reports a diagnosis of AMD at follow-up is eligible.

5.3 Participants must be informed of the investigational nature of this study and must sign and give written informed consent in accordance with institutional and federal guidelines before SEE procedures are initiated. Participants must have signed an applicable medical records release form and it must have been sent to [name] at the SELECT Eye Endpoints (SEE) Center in Boston, MA by FAX ([contact]) immediately after registration to SEE.

5.4 At the time of participant registration, the treating institution's name and ID number must be provided to the Statistical Center in order to ensure that the current (within 365 days) date of institutional review board approval for this study has been entered into the data base.

6.0 STRATIFICATION FACTORS

Stratification factors are not applicable to this study.

7.0 TREATMENT PLAN

All participants will receive treatment as outlined in **S0000**.

Please refer all questions regarding any procedures related to **S0000B** (SEE) to [name] at [name].

Detailed procedures for the Baseline Visit and Six Month and Annual Visits can be found in the **S0000B** (SEE) Study Manual, which is Appendix K of the SELECT Study Manual.

7.1 Baseline Visit

Participant information on previous diagnoses of cataract and AMD are collected as part of the baseline examination in SELECT. For SEE, medical record data will be collected (as described below) to confirm the baseline reports of AMD, but will not be collected for baseline reports of cataract or cataract surgery.

7.2 Six Month and Annual Visits

Participant reports of new diagnoses of cataract and AMD made since the start of **S0000B** (SEE) are collected at the SELECT Six Month and Annual Visits. This is accomplished through additional questions on Form 202 - Medical Events and on Form 208 - Prostate Cancer Follow-Up.

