7.3 Medical Record Release

Participants who report a diagnosis of AMD at baseline, or a diagnosis of AMD at a SELECT Six Month or Annual Visit will be requested to complete a medical record release form on which they indicate the treating eye doctor(s) and provide written consent for the SELECT Eye Endpoints (SEE) Center to review the relevant medical records. The Study Site will register the participant to **S0000B** (SEE) via the SELECT workbench and then immediately fax the medical release form to the SELECT Eye Endpoints (SEE) Center in Boston, MA ([contact]). If the participant is unable to provide sufficient information about the event and the treating eye doctor(s) while at the Study Site, the participant will be asked to complete the form at home and return it to the Study Site in a self-addressed stamped envelope. The Study Site will register the participant to **S0000B** (SEE) and then immediately fax the form to the SEE Center. As an alternative to faxing the medical release form to the SEE Center, depending on Study Site local requirements, the Study Site may request the medical records from the ophthalmologist/optometrist, collect the detailed questionnaire and forward all materials obtained to the SEE Center (see Section 10.0).

7.4 Criteria for removal from protocol:

The participant may withdraw from the study at any time for any reason.

7.5 The participant will be followed as described in the main SELECT protocol (S0000**).**

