Ophthalmologists and optometrists may supply the requested information by providing photocopies of the relevant medical records instead of completing the forms.

Once obtained, the questionnaires and medical records will be reviewed by the Study Coordinator to determine their conformity with uniform diagnostic criteria.

Three categories of the AMD endpoint are defined: (a) AMD - self-report confirmed by medical record evidence of a diagnosis of AMD subsequent to randomization to SELECT (S0000); (b) AMD with vision loss - as in (a) but with vision loss to 20/30 or worse attributable to AMD (visually-significant AMD); (c) advanced AMD - as in (b), but including evidence of geographic atrophy or exudative disease.

The primary AMD endpoint in this eye study, visually-significant AMD, will, on average, represent a less severe stage of disease than cases meeting the criteria for advanced AMD in AREDS. In our other ongoing trials in men and women (Physicians' Health Study, Women's Health Study, Women's Antioxidant Cardiovascular Study) approximately 60 - 65% of cases meeting the criteria of vision loss to 20/30 or worse attributable to AMD are characterized by early signs of AMD only (i.e. some combination of drusen and/or retinal pigment epithelium changes). Thus, the primary AMD endpoint of visually-significant AMD will provide a meaningful test of whether antioxidant vitamins can be effective in lowering risks of earlier stages of AMD. In secondary analyses, we propose to examine whether the study agents reduce the risk of advanced AMD (cases with evidence of geographic atrophy or exudative disease) as well as total AMD including cases with and without vision loss.

Two cataract endpoints are defined: (a) cataract - self-report confirmed by medical record evidence of a diagnosis of age-related cataract subsequent to randomization to SELECT (S0000), with best-corrected visual acuity of 20/30 or worse due to cataract; (b) extraction - surgical removal of an incident cataract.

The primary cataract endpoint in this eye study provides a meaningful test of whether antioxidant vitamins can be effective in lowering risks of visually significant lens opacities. In secondary analyses, we propose to examine whether the study agents reduce the risk of cataract surgery as well as subtypes.

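### Does Section 7.2 drop eye diagnoses made between SELECT randomization and the start of SEE?

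*Combined protocol and SAP*

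**What the plan says.** Section 7.2 states that the SELECT Six Month and Annual Visits collect "Participant reports of new diagnoses of cataract and AMD made since the start of" SEE, and adds: "This is accomplished through additional questions on Form 202 - Medical Events" (and on Form 208).

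Section 10.0 defines the AMD endpoint as "self-report confirmed by medical record evidence of a diagnosis of AMD subsequent to randomization to SELECT". For cataract it requires "medical record evidence of a diagnosis of age-related cataract subsequent to randomization to SELECT", with acuity of 20/30 or worse due to cataract.

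Section 5.1 says: "Participants may be registered to SEE at any time after SELECT randomization". Section 5.2 begins "The potential participant must report a diagnosis of age-related macular degeneration (AMD) at baseline (contact 010) or at follow-up" and also admits a cataract diagnosis or extraction reported at follow-up. It sets no date limit on the follow-up diagnosis, but it does not itself name randomization as a starting point.

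Section 7.1 deals with earlier history: "Participant information on previous diagnoses of cataract and AMD are collected as part of the baseline examination in SELECT". Section 7.0 refers the reader to the SEE Study Manual for detailed visit procedures.

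**The concern.** Read quickly, Section 7.2 uses a different starting date from Section 10.0. The endpoints count from SELECT randomization, whereas Section 7.2 seems to collect only diagnoses dated after SEE began. The baseline history in Section 7.1 covers only what preceded randomization. Section 11.1, assumption b, uses the ages of men already randomized in July-December 2001, so some men probably entered SELECT before SEE was in place.

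On that reading, a diagnosis in the interval would be caught by neither the baseline examination nor the follow-up questions. The man would stay in the risk set as event-free, with person-time still accruing from randomization. The trial would lose primary-endpoint events and slightly understate absolute incidence, and the power in Section 11.1, which rests on the full disease-free cohorts, would be a little optimistic.

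**Working it through.** **1. Which reading fits the other sections?** The phrase about the start of SEE can attach to either of two nouns.

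| Section | If it describes the diagnoses | If it describes the reports |
|---|---|---|
| 5.1, registration any time after randomization | compatible | compatible |
| 5.2, no date limit on follow-up diagnoses | adds a limit that 5.2 lacks | agrees |
| 7.3, release form for any AMD reported at a visit ("a diagnosis of AMD at a SELECT Six Month or Annual Visit will be requested to complete a medical record release form") | adds a limit that 7.3 lacks | agrees |
| 10.0, diagnoses after randomization | conflicts | agrees |

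On the second reading, Section 7.2 only says when the added questions came into use. No other section makes the start of SEE a boundary for an endpoint.

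**2. What happens to a diagnosis in the interval that is reported later?** The Section 10.0 questionnaires ask the eye doctor for the date of first diagnosis, the date acuity reached 20/30 or worse and, for cataract, the extraction date. The endpoint definition then counts any confirmed diagnosis after randomization. A late report is therefore dated and counted. A later extraction is a separate trigger under Section 5.2.

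**3. How large is the loss if nothing is recovered?**

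Inputs from Section 11.1: 31,580 men free of AMD at 3 events per 1,000 person-years; 30,250 free of cataract at 10 per 1,000; loss 0.05 per year; two-sided 0.05; Lachin-Foulkes formulas. The SEE start date is not stated. The gap is taken as 5 months (the earlier accrual evidenced in assumption b), with 1 year as an assumed wider case.

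Accrual patterns, with uniform entry over R years and T years in total:
- A: R = 5, T = 12. This is an assumption, chosen because it reproduces the AMD column.
- B: R = 3, T = 10. This follows assumption d.

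Reproducing the plan's AMD power column (RR 0.85, 0.80, 0.75, 0.70, 0.65):
- Stated: 54.4, 79.9, 94.4, 99.1, 99.9
- A: 54.4, 79.9, 94.4, 99.1, 99.9
- B: 51.0, 76.5, 92.5, 98.5, 99.8

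For cataract at RR 0.85, A gives 95.4% and B gives 93.8%. Neither equals the stated 92.0%.

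With event rate λ, loss rate η, entry time u and lost time a = max(gap − u, 0), the captured event probability is

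λ/(λ+η) × [exp(−(λ+η)a) − exp(−(λ+η)(T−u))], averaged over u.

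A hand check for AMD at RR 0.80 uses the average rate (0.003 + 0.0024)/2 = 0.0027 and a 5-month gap. The men affected lose on average half of 5/12 year, or 0.208 years.
- A: 31,580 × (5/12)/5 = 2,632 men; × 0.208 = 548 person-years; × 0.0027 = 1.5 events.
- B: 31,580 × (5/12)/3 = 4,386 men; × 0.208 = 914 person-years; × 0.0027 = 2.5 events (2.4 in the full formula, which allows for loss to follow-up).

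Full formula:

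| Gap | Pattern | AMD events lost | AMD power, RR 0.80 | Cataract events lost, RR 0.85 |
|---|---|---|---|---|
| 5 months | A | 1.5 of 634 (0.2%) | 79.9% to 79.8% | 4.8 of 2,022 |
| 5 months | B | 2.4 of 583 (0.4%) | 76.5% to 76.3% | 8.0 of 1,864 |
| 1 year | A | 8 of 634 (1.3%) | 79.9% to 79.4% | 27 of 2,022 |
| 1 year | B | 14 of 583 (2.4%) | 76.5% to 75.5% | 46 of 1,864 |

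The AMD placebo rate moves from 3.00 to 2.99 per 1,000 at 5 months, and to 2.96 (A) or 2.93 (B) at 1 year. A true rate ratio of 0.8000 becomes 0.8001 even at 1 year, because the capture rule does not depend on assignment.

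**The case for a change.** The best case for acting is that the wording is loose on either reading. If the phrase describes the reports, Section 7.2 still gives no look-back period, so a site relying on that sentence alone would not know to ask back to randomization. Medical records are requested only after a man reports something, so an interval diagnosis that is never reported is never found. SEE may also have opened later than assumed: a gap of 2 to 3 years would cost 5% to 21% of AMD events and 2 to 10 points of power. Aligning one sentence would cost almost nothing.

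It is fair that the sentence could be clearer. The rest carries less weight. Sites work from Forms 202 and 208 and the Study Manual, none of which is in the document, so failure to ask cannot be inferred. Nothing in the document supports a gap of 2 to 3 years. A cruder calculation that removes the first half-year of events from every man (AMD power 78% to 75%, fixed 8.8 years) overstates the matter, since only men randomized before SEE opened could lose anything.

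An analysis remedy would be harder to defend than the sentence. Starting at-risk time at the opening of SEE would give no person-time to men who had already left SELECT. That departs from the intention-to-treat rule in Section 11.3 for the sake of 0.09% (A) or 0.14% (B) of men at a 5-month gap.

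**Conclusion.** No change follows. Section 7.2 is ambiguous, but one of its two ordinary readings agrees with Sections 5.1, 5.2, 7.3 and 10.0. Section 10.0 alone defines the endpoints, and it does so from SELECT randomization. Section 11.3 points the same way when it refers to early years after randomization. An analyst would count confirmed diagnoses from that date without further instruction.

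Even on the unfavourable reading, with no interval diagnosis ever recovered, the evidenced 5-month gap costs 0.2% to 0.4% of AMD events and 0.1 to 0.2 points of power. The two accrual patterns differ by 3.4 points (79.9% against 76.5%) with no gap at all, which exceeds the effect of any gap up to 1 year. The treatment comparison is essentially unaffected.

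This rests on the gap being close to the 5 months that Section 11.1 evidences, on uniform accrual, and on capture being independent of treatment assignment, as randomization makes likely. The SEE start date and the form wording are not in the document, so the actual loss, if any, cannot be calculated.

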7.3 Medical Record Release

Participants who report a diagnosis of AMD at baseline, or a diagnosis of AMD at a SELECT Six Month or Annual Visit will be requested to complete a medical record release form on which they indicate the treating eye doctor(s) and provide written consent for the SELECT Eye Endpoints (SEE) Center to review the relevant medical records. The Study Site will register the participant to **S0000B** (SEE) via the SELECT workbench and then immediately fax the medical release form to the SELECT Eye Endpoints (SEE) Center in Boston, MA ([contact]). If the participant is unable to provide sufficient information about the event and the treating eye doctor(s) while at the Study Site, the participant will be asked to complete the form at home and return it to the Study Site in a self-addressed stamped envelope. The Study Site will register the participant to **S0000B** (SEE) and then immediately fax the form to the SEE Center. As an alternative to faxing the medical release form to the SEE Center, depending on Study Site local requirements, the Study Site may request the medical records from the ophthalmologist/optometrist, collect the detailed questionnaire and forward all materials obtained to the SEE Center (see Section 10.0).

7.4 Criteria for removal from protocol:

The participant may withdraw from the study at any time for any reason.

7.5 The participant will be followed as described in the main SELECT protocol (S0000**).**

